8.3. Adverse Events, Serious Adverse Events, and Other Safety Reporting

The definitions of an AE and an SAE can be found in [Appendix 3](#).

AEs may arise from symptoms or other complaints reported to the investigator by the participant (or, when appropriate, by a caregiver, surrogate, or the participant's legally authorized representative), or they may arise from clinical findings of the Investigator or other healthcare providers (clinical signs, test results, etc.).

The investigator and any qualified designees are responsible for detecting, documenting, and recording events that meet the definition of an AE or SAE and remain responsible to pursue and obtain adequate information both to determine the outcome and to assess whether the event meets the criteria for classification as an SAE or caused the participant to discontinue the study intervention (see [Section 7.1](#)).

During the active collection period as described in [Section 8.3.1](#), each participant will be questioned about the occurrence of AEs in a nonleading manner.

In addition, the investigator may be requested by Pfizer Safety to obtain specific follow-up information in an expedited fashion.

8.3.1. Time Period and Frequency for Collecting AE and SAE Information

The time period for actively eliciting and collecting AEs and SAEs (“active collection period”) for each participant begins from the time the participant provides informed consent, which is obtained before the participant’s participation in the study (ie, before undergoing any study-related procedure and/or receiving study intervention), through and including a minimum of 5 months after the last administration of the study intervention.

Since this is an extension study, once the ICD is signed, any newly developed adverse events recorded prior to study drug dosing should be recorded in the participant’s medical history. Once the participant receives study drug, all and any adverse events will be reviewed and recorded on the adverse event page.

Follow-up by the investigator continues throughout and after the active collection period and until the AE or SAE or its sequelae resolve or stabilize at a level acceptable to the investigator.

For participants who are screen failures, the active collection period ends when screen failure status is determined.

If the participant withdraws from the study and also withdraws consent for the collection of future information, the active collection period ends when consent is withdrawn.

If a participant permanently discontinues or temporarily discontinues study intervention because of an AE or SAE, the AE or SAE must be recorded on the CRF and the SAE reported using the CT SAE Report Form.

Investigators are not obligated to actively seek information on AEs or SAEs after the participant has concluded study participation. However, if the investigator learns of any SAE, including a death, at any time after a participant has completed the study, and he/she considers the event to be reasonably related to the study intervention, the investigator must promptly report the SAE to Pfizer using the CT SAE Report Form.

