2.2.1.1.2. PK Summary for C0251001

Following single IV infusion dosing of PF-06823859, exposure based on AUC_{inf} and C_{max} exhibited approximately dose-proportional increase with increasing doses across the dose ranges from 30 mg to 2000 mg. Geometric mean CL was slow with values ranging from 0.006 to 0.007 L/hr across all doses, and small V_{ss} values (geometric mean values ranging from 4.8 L to 6.0 L) indicative of distribution primarily in the plasma volume. Mean $t_{1/2}$ values were similar across the doses ranging from 23 to 29 days.

Following multiple SC doses of 100 mg and 300 mg administered Q2W for a total of 3 doses, peak serum concentrations were achieved with a median T_{max} of 96 hours post dose on Day 1, and 48 hours post dose on Day 15 and Day 29. No marked departures from dose proportionality were observed for AUC_{τ} and C_{max} for the 2 dose regimens. R_{ac} for serum AUC_{τ} and C_{max} were <2.5 fold and mean $t_{1/2}$ values ranging from 25 to 35 days. CL/F was similar across the 2 dose regimens with geometric mean estimates at 0.016 L/h, while the geometric mean V_z/F estimates were approximately similar ranging from 13.9 to 18.9 L.

Estimated bioavailability values based on geometric mean AUC_{τ} for the 100 mg and 300 mg SC doses on Day 1 were 43% and 44%, respectively, relative to the corresponding IV doses in the SAD period.

Following multiple IV doses of 600 mg administered Q2W for a total of 3 doses; geometric mean AUC_{τ} values were slightly higher on Days 15 and 29 compared to that observed on Day 1 with similar C_{max} values observed across all dosing days. Serum AUC_{τ} for the 600 mg IV (Q4W) \times 2 doses treatment group was slightly higher compared to AUC_{τ} from the 600 mg IV (Q2W) \times 3 doses treatment group on Day 1 and Day 29. Multiple IV dose PK results were generally consistent with single dose IV PK data. R_{ac} for serum AUC_{τ} and C_{max} were <1.9 fold and mean $t_{1/2}$ of 27 and 28 days was observed following 600 mg IV Q2W and 600 mg IV Q4W dosing, respectively.

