4. STUDY DESIGN

4.1. Overall Design

This is a Phase 2b, OLE study to evaluate the long-term safety and tolerability of PF-06823859 in adult participants with moderate to severe DM who completed the treatment period of a qualifying study (including Protocol C0251002) and have agreement from their study doctor to continue active treatment. Eligible participants will not have had any significant protocol deviations (eg, not following the protocol, taking prohibited medications, not using appropriate contraception) or have not completed all study treatment in the qualifying study. Approximately 30 participants who complete the Week 24 visit during the treatment period in Study C0251002 or equivalent in another qualifying study, may be

enrolled in Protocol C0251008. The treatment duration of OLE study participation will be up to 48 weeks (treatment period is up through and including Week 52), with a 16 week follow up period. See [Section 1.2](#) for the study schematic.

Qualified participants will be randomized to receive open-label PF-06823859 600 mg IV every 4 weeks for up to 48 weeks, however the treatment period is up to Week 52. All participants will be followed for another 16 weeks in the Follow-up Period. Participants who are discontinued from study intervention will also enter the follow-up period.

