8.3.5.1. Exposure During Pregnancy

An EDP occurs if:

- A female participant is found to be pregnant while receiving or after discontinuing study intervention.
- A male participant who is receiving or has discontinued study intervention exposes a female partner prior to or around the time of conception.
- A female is found to be pregnant while being exposed or having been exposed to study intervention due to environmental exposure. Below are examples of environmental EDP:
 - A female family member or healthcare provider reports that she is pregnant after having been exposed to the study intervention by accidental needle stick during drug preparation.
 - A male family member or healthcare provider who has been exposed to the study intervention by accidental needle stick during drug preparation then exposes his female partner prior to or around the time of conception.

The investigator must report EDP to Pfizer Safety within 24 hours of the investigator's awareness, irrespective of whether an SAE has occurred. The initial information submitted should include the anticipated date of delivery (see below for information related to termination of pregnancy).

- If EDP occurs in a participant or a participant's partner, the investigator must report this information to Pfizer Safety on the CT SAE Report Form and an EDP Supplemental Form, regardless of whether an SAE has occurred. Details of the pregnancy will be collected after the start of study intervention and until at least 5 terminal half-lives after the last dose. This time would be approximately 20 weeks or 5 months after the last dose of study intervention.

- If EDP occurs in the setting of environmental exposure, the investigator must report information to Pfizer Safety using the CT SAE Report Form and EDP Supplemental Form. Since the exposure information does not pertain to the participant enrolled in the study, the information is not recorded on a CRF; however, a copy of the completed CT SAE Report Form is maintained in the investigator site file.

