10.4.2. Female Participant Reproductive Inclusion Criteria

A female participant is eligible to participate if she is not pregnant or breastfeeding, and at least 1 of the following conditions applies:

- Is not a WOCBP (see definitions below in [Section 10.4.3](#)).

OR

- Is a WOCBP and using a contraceptive method that is highly effective (with a failure rate of <1% per year), preferably with low user dependency, as described below during the intervention period and for at least 150 days after the last dose of study intervention, which corresponds to the time needed to eliminate any reproductive safety risk of the study intervention(s). The investigator should evaluate the effectiveness of the contraceptive method in relationship to the first dose of study intervention.

- Is a WOCBP and using a contraceptive method that is highly effective (with a failure rate of <1% per year), with high user dependency, as described below during the intervention period and for at least 150 days after the last dose of study intervention, which corresponds to the time needed to eliminate any reproductive safety risk of the study intervention(s). In addition, a second effective method of contraception, as described below, must be used. The investigator should evaluate the effectiveness of the contraceptive method in relationship to the first dose of study intervention.

The investigator is responsible for review of medical history, menstrual history, and recent sexual activity to decrease the risk for inclusion of a woman with an early undetected pregnancy.

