Any participant meeting discontinuation criteria must enter follow-up with their first follow-up visit occurring 1 week after their last dose whenever possible, until the event has returned to normal or baseline levels or is deemed clinically stable. The procedures scheduled for the early withdrawal visit will be performed on the last day the participant takes the study intervention or as soon as possible thereafter. The only exception to this is when a participant specifically withdraws consent for any further contact with him/her or persons previously authorized by the participant to provide this information.

Participants will be followed post drug discontinuation for 5 terminal half-lives. Additional follow-up visits may occur as needed until any clinically relevant abnormalities or adverse events have resolved, returned to a baseline state, or are deemed clinically stable.

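### Active AE collection must run at least 5 months after the last dose, but the schedule stops at 140 days, and the follow-up length for early discontinuers is not reconciled between sections

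*Protocol*

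**What the plan says.** The post-dose period is set in several places in the protocol.

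- **Section 8.3.1** runs active AE and SAE collection from consent "through and including a minimum of 5 months after the last administration of the study intervention". The same section says investigators need not actively look for events once a participant has finished the study.
- **Section 4.1** (and the synopsis, 1.1) describes the "treatment period is up through and including Week 52), with a 16 week follow up period" and adds: "All participants will be followed for another 16 weeks in the Follow-up Period". Participants taken off study drug enter that same period.
- **Section 1.3, Tables 1 and 2** show 13 doses from Day 1 to Week 48. AE monitoring, contraception checks and urine pregnancy tests run to Week 68. **Section 4.4** makes the Week 68 visit the point of completion.
- **Section 8.3.5.1** collects pregnancy details for at least 5 terminal half-lives: "This time would be approximately 20 weeks or 5 months after the last dose of study intervention". **Section 10.4.1** converts the same 5 half-lives to about 150 days, and **Section 10.4.2** requires contraception "for at least 150 days after the last dose of study intervention".
- **Section 10.10.2** covers participants who meet discontinuation criteria. They have their "first follow-up visit occurring 1 week after their last dose whenever possible", and then: "Participants will be followed post drug discontinuation for 5 terminal half-lives".
- **Section 2.2.1.1.2** reports that a mean half-life of "27 and 28 days was observed following 600 mg IV Q2W and 600 mg IV Q4W dosing", and 23 to 29 days after single IV doses.

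The SAP (Section 9.1) gives Week 48 as Day 337 (window 334 to 340) and Week 68 as Day 477 (window 474 to 480).

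**The concern.** Safety is the primary objective, and AE incidence is reported as counts and percentages (SAP Section 6.1.1) over treatment plus follow-up (SAP Section 6.6). The length of post-dose observation is therefore part of what is measured. The SAP's treatment-emergent definition (Section 3.1.1) refers to an effective duration of treatment without giving a number of days, so it does not settle the window either.

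A site that follows the schedule exactly closes a completer's participation before the Section 8.3.1 minimum has passed. From then on, that section no longer obliges it to ask about events. For someone who stops early, one section points to 16 weeks and another to 5 half-lives, and no visit in either schedule is tied to the second rule. Sites could then observe discontinuers for different lengths of time, with those differences carried into the percentages unadjusted.

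**Working it through.** **1. The protocol's own conversion.** Section 8.3.5.1 equates 5 half-lives with about 20 weeks. With the 28 days reported for 600 mg IV every 4 weeks, 5 x 28 = 140 days and 140 / 7 = 20.0 weeks. The figure is reproduced. The 150 days in Section 10.4.1 implies 150 / 5 = 30 days, above every IV half-life in Section 2.2.1.1.2.

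**2. Completers: time from last dose to last AE contact.**
- At target days: 477 - 337 = 140 days (20 weeks). The 16 weeks start at Week 52, four weeks after the last dose.
- Shortest and longest within windows: 474 - 340 = 134; 480 - 334 = 146.

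**3. Completers against the 5-month minimum.** Month length is an assumption: 30 days gives 150, and 30.44 days gives 152.
- At target dates: 150 - 140 = 10 and 152 - 140 = 12 days short.
- In the most favourable case within windows: 150 - 146 = 4 days short. No on-schedule completer reaches the minimum.
- Collection would have to run to Day 337 + 150 = 487, or Day 337 + 152 = 489.

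**4. Completers against 5 half-lives.**

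| Half-life (days) | 5 half-lives (days) | 140 minus this |
|---|---|---|
| 23 (single IV, low) | 115 | +25 |
| 27 (600 mg IV every 2 weeks) | 135 | +5 |
| 28 (600 mg IV every 4 weeks) | 140 | 0 |
| 29 (single IV, high) | 145 | -5 |
| Section 10.4.1 figure | 150 | -10 |

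For the half-life of the regimen used here, completers meet the rule at target dates.

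**5. Early discontinuers: 16 weeks (112 days) from different starting points.** The start is not stated, so each row is an assumption.

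| Start of the 16 weeks | Last day after dose | Against 115 / 135 / 140 / 145 days |
|---|---|---|
| Last dose | 112 | -3 / -23 / -28 / -33 |
| First follow-up visit, 1 week after last dose | 7 + 112 = 119 | +4 / -16 / -21 / -26 |
| 4 weeks after last dose, as for completers | 28 + 112 = 140 | +25 / +5 / 0 / -5 |

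On the first row, 112 / 28 = 4.0 half-lives, which is short at every reported IV value. Against the 5-month minimum it is 150 - 112 = 38 to 152 - 112 = 40 days short.

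**6. Is there another route to the missing days?** The schedules' extension after the last visit applies only to participants with anti-drug antibodies and AEs attributed to immunogenicity. Section 8.7.2 adds an optional return for participants with positive results. Neither covers everyone.

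**7. Pregnancy-related checks.** Scheduled contraception checks and pregnancy tests end at day 140, while contraception is required for 150 days.

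**The case against.** The best defence is that the protocol treats 20 weeks and 5 months as roughly the same (Section 8.3.5.1), so the completers' gap is partly rounding, and that Section 10.10.2 does require 5 half-lives for discontinuers, so no requirement is missing. Both points have weight. However, Section 8.3.1 states a minimum rather than an approximation, and the rule in Section 10.10.2 sits beside a 16-week period with no visit linking them.

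Several stronger readings are tempting, and the documents do not support them.

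- *Completers miss 5 half-lives.* At the 28-day half-life for this regimen they meet them. They miss only at 29 days or on the 150-day figure.
- *Discontinuers are followed only to day 91.* A reader might infer this from a first visit at 1 week and 4-weekly visits after that: (1 + 12) x 7 = 91. No section states that pattern, and Section 10.10.2 requires 5 half-lives and allows further visits.
- *Discontinuers certainly get the shortest observation.* That depends on the unstated start. One plausible start gives the same 140 days as completers.
- *They mostly stop because of AEs.* No section gives the mix of reasons. Flare, added immunosuppressants, prohibited medication and lack of efficacy are other routes.
- *Pregnancy follow-up stops early.* The 150 days is a contraception undertaking. Section 8.3.5.1 allows about 20 weeks for collecting pregnancy details, and known pregnancies are followed to completion.
- *AE incidence is materially biased.* Nothing in the documents allows the effect of 10 to 12 days to be estimated.

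**Conclusion.** Wrong as written, on two internal contradictions. First, the 5-month minimum in Section 8.3.1 is not delivered by a schedule whose last AE contact is 140 days after the last dose. The shortfall is 10 to 12 days at target dates, assuming months of 30 to 30.44 days, and it persists throughout the visit windows. Second, for early discontinuers the 16 weeks of Section 4.1 and the 5 half-lives of Section 10.10.2 are not reconciled. If the 16 weeks run from the last dose, follow-up ends 3 to 33 days before 5 half-lives across the reported IV values. If they start 4 weeks later, it equals 5 half-lives at 28 days. The first contradiction is firm but small. The size of the second depends on a starting point the protocol does not give, and that omission is part of the defect. The two conversions of 5 half-lives, about 20 weeks and about 150 days, add to the inconsistency.

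**What to change.** Sections 1.1/4.1, 1.3 (both schedules), 8.3.1, 8.3.5.1, 10.4 and 10.10.2 must be reconciled. After that, the AE collection window should be counted from the last dose, be the same in every section for completers and for early discontinuers, and match the last scheduled AE contact. The protocol should state when a discontinuer's follow-up starts and which visits deliver it, and should use one conversion of 5 terminal half-lives throughout. The sponsor chooses the duration. The treatment-emergent definition in SAP Section 3.1.1 can then refer to that window.

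The cost is protocol wording. Depending on the length chosen, it may also mean at most one further contact for each of about 30 participants.

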8.3.1.1. Reporting SAEs to Pfizer Safety

All SAEs occurring in a participant during the active collection period as described in [Section 8.3.1](#) are reported to Pfizer Safety on the CT SAE Report Form immediately upon awareness and under no circumstance should this exceed 24 hours, as indicated in [Appendix 3](#). The investigator will submit any updated SAE data to the sponsor within 24 hours of it being available.

8.3.1.2. Recording Nonserious AEs and SAEs on the CRF

All nonserious AEs and SAEs occurring in a participant during the active collection period, which begins after obtaining informed consent as described in [Section 8.3.1](#), will be recorded on the AE section of the CRF.

The investigator is to record on the CRF all directly observed and all spontaneously reported AEs and SAEs reported by the participant.

8.3.2. Method of Detecting AEs and SAEs

The method of recording, evaluating, and assessing causality of AEs and SAEs and the procedures for completing and transmitting SAE reports are provided in [Appendix 3](#).

Care will be taken not to introduce bias when detecting AEs and/or SAEs. Open-ended and nonleading verbal questioning of the participant is the preferred method to inquire about AE occurrences.

8.3.3. Follow-Up of AEs and SAEs

After the initial AE or SAE report, the investigator is required to proactively follow each participant at subsequent visits/contacts. For each event, the investigator must pursue and obtain adequate information until resolution, stabilization, the event is otherwise explained, or the participant is lost to follow-up (as defined in [Section 7.3](#)).

In general, follow-up information will include a description of the event in sufficient detail to allow for a complete medical assessment of the case and independent determination of possible causality. Any information relevant to the event, such as concomitant medications and illnesses, must be provided. In the case of a participant death, a summary of available autopsy findings must be submitted as soon as possible to Pfizer Safety.

Further information on follow-up procedures is given in [Appendix 3](#).

8.3.4. Regulatory Reporting Requirements for SAEs

Prompt notification by the investigator to the sponsor of an SAE is essential so that legal obligations and ethical responsibilities toward the safety of participants and the safety of a study intervention under clinical investigation are met.

The sponsor has a legal responsibility to notify both the local regulatory authority and other regulatory agencies about the safety of a study intervention under clinical investigation. The sponsor will comply with country-specific regulatory requirements relating to safety reporting to the regulatory authority, IRBs/ECs, and investigators.

Investigator safety reports must be prepared for SUSARs according to local regulatory requirements and sponsor policy and forwarded to investigators as necessary.

An investigator who receives SUSARs or other specific safety information (eg, summary or listing of SAEs) from the sponsor will review and then file it along with the SRSD(s) for the study and will notify the IRB/EC, if appropriate according to local requirements.

8.3.5. Environmental Exposure, Exposure During Pregnancy or Breastfeeding, and Occupational Exposure

Environmental exposure occurs when a person not enrolled in the study as a participant receives unplanned direct contact with or exposure to the study intervention. Such exposure may or may not lead to the occurrence of an AE or SAE. Persons at risk for environmental exposure include healthcare providers, family members, and others who may be exposed. An environmental exposure may include exposure during pregnancy, exposure during breastfeeding, and occupational exposure.

Any such exposure to the study intervention under study are reportable to Pfizer Safety within 24 hours of investigator awareness.

8.3.5.1. Exposure During Pregnancy

An EDP occurs if:

- A female participant is found to be pregnant while receiving or after discontinuing study intervention.
- A male participant who is receiving or has discontinued study intervention exposes a female partner prior to or around the time of conception.
- A female is found to be pregnant while being exposed or having been exposed to study intervention due to environmental exposure. Below are examples of environmental EDP:
 - A female family member or healthcare provider reports that she is pregnant after having been exposed to the study intervention by accidental needle stick during drug preparation.
 - A male family member or healthcare provider who has been exposed to the study intervention by accidental needle stick during drug preparation then exposes his female partner prior to or around the time of conception.

The investigator must report EDP to Pfizer Safety within 24 hours of the investigator's awareness, irrespective of whether an SAE has occurred. The initial information submitted should include the anticipated date of delivery (see below for information related to termination of pregnancy).

- If EDP occurs in a participant or a participant's partner, the investigator must report this information to Pfizer Safety on the CT SAE Report Form and an EDP Supplemental Form, regardless of whether an SAE has occurred. Details of the pregnancy will be collected after the start of study intervention and until at least 5 terminal half-lives after the last dose. This time would be approximately 20 weeks or 5 months after the last dose of study intervention.

- If EDP occurs in the setting of environmental exposure, the investigator must report information to Pfizer Safety using the CT SAE Report Form and EDP Supplemental Form. Since the exposure information does not pertain to the participant enrolled in the study, the information is not recorded on a CRF; however, a copy of the completed CT SAE Report Form is maintained in the investigator site file.

Follow-up is conducted to obtain general information on the pregnancy and its outcome for all EDP reports with an unknown outcome. The investigator will follow the pregnancy until completion (or until pregnancy termination) and notify Pfizer Safety of the outcome as a follow-up to the initial EDP Supplemental Form. In the case of a live birth, the structural integrity of the neonate can be assessed at the time of birth. In the event of a termination, the reason(s) for termination should be specified and, if clinically possible, the structural integrity of the terminated fetus should be assessed by gross visual inspection (unless preprocedure test findings are conclusive for a congenital anomaly and the findings are reported).

Abnormal pregnancy outcomes are considered SAEs. If the outcome of the pregnancy meets the criteria for an SAE (ie, ectopic pregnancy, spontaneous abortion, intrauterine fetal demise, neonatal death, or congenital anomaly in a live-born baby, a terminated fetus, an intrauterine fetal demise, or a neonatal death), the investigator should follow the procedures for reporting SAEs. Additional information about pregnancy outcomes that are reported to Pfizer Safety as SAEs follows:

- Spontaneous abortion including miscarriage and missed abortion;
- Neonatal deaths that occur within 1 month of birth should be reported, without regard to causality, as SAEs. In addition, infant deaths after 1 month should be reported as SAEs when the investigator assesses the infant death as related or possibly related to exposure to the study intervention.

Additional information regarding the EDP may be requested by the sponsor. Further follow-up of birth outcomes will be handled on a case-by-case basis (eg, follow-up on preterm infants to identify developmental delays). In the case of paternal exposure, the investigator will provide the participant with the Pregnant Partner Release of Information Form to deliver to his partner. The investigator must document in the source documents that the participant was given the Pregnant Partner Release of Information Form to provide to his partner.

